13.2 Endpoint Assessments

13.2.1 Primary Clinical Endpoint

The primary endpoint will be the week-52 eGFR. Mean eGFR of the belatacept group will be compared to the mean eGFR of the tacrolimus reference group within a mixed models repeated measures (MMRM) framework , wherein repeated measures of eGFR at weeks 4, 12, 28, 36 and 52 will be modeled as a linear function of time (and perhaps other baseline covariates) in the 2 treatment groups. At week-52, a contrast will be made between the eGFR mean of the belatacept group and the eGFR mean of the tacrolimus group. ANCOVA assumptions will be evaluated graphically via standard residual analyses. If the assumptions fail, a suitable transformation (e.g., natural logarithms) will be found and the data will be reanalyzed on the transformed scale. Results will be reported with p-values associated with the F-test for each contrast and the corresponding mean treatment differences with two-sided 95% confidence intervals. All tests of significance will be two-tailed at the 0.05 level.

Estimating the contrasts within the repeated measures framework will provide treatment comparisons that are robust to subject dropout bias as long as the dropout pattern is missing at random²⁷. Data are missing at random whenever the "missingness" mechanism is a function of observable relationships among the nonmissing responses and covariates. Using the methods of Ma et al.²⁸, we will evaluate the MAR assumption in the data prior to implementing the MMRM analysis. If the MAR assumption fails, we will consider more robust alternatives (e.g., pattern mixture modeling)²⁹.

A number of studies have shown RMANCOVA to be superior to analyses of completers or of data with LOCF imputations³⁰. Nonetheless, we will conduct 2 related sensitivity analyses: (1) replace the missing week-52 values with the corresponding nonmissing week 36 values of each subject, dropping anyone who is missing both week-36 and week-52 and perform the ANCOVA as currently specified; (2) include only the completers in the ANCOVA analysis (i.e., exclude all dropouts). The sensitivity analyses will be included as additional secondary analyses.

13.2.2 Secondary Clinical Endpoints

The secondary endpoints are defined in Protocol section 1.5.

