13.3 Sample Size and Power Calculations

We have used data from the belatacept phase II and DIRECT studies and from the literature (Grewal and Blake 2005) to provide expected values for the GFR standard deviations shown in Table 10 below. Sample size calculations for these analyses were performed using NCSS-PASS software.

In the primary endpoint analysis, we will compare the mean GFR between the study groups at 12 months. With the sample sizes fixed, a priori, at 30 subjects in each of the two treatment arms, the following table shows the smallest treatment mean GFR differences (i.e. effect sizes) we will be able to declare significantly different, with 80% power and Type I error rates of 0.05 and 0.10:

Table 11 - Smallest Detectable Difference in GFR at 12 Months for Different Standard Deviationsand Alpha Levels

GFR Standard Deviation	Alpha Level	Smallest Detectable Difference in GFR (mL/min/1.7 m ²)
16	0.05	12.0
	0.10	10.5
20	0.05	15.0
	0.10	13.0
24	0.05	18.0
	0.10	16.0

This study has been powered to be able to detect minimum detectable differences in the primary endpoint at both the 0.05 and 0.10 levels that are clinically relevant as shown in Table 9 above. When reporting results of the primary endpoint analysis, we will report a p-value as significant at the 0.10 level if it is less than 0.10 and as significant at the 0.05 level if it is less than 0.05. As previously stated, all secondary endpoint analyses will be performed at the 0.05 level.

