Monitoring Assay Development: BLOOD	Vacutainer Tube			Л		Л				Л		~				л	Λ
Viral Monitoring by PCR (CMV, BKV, JCV, HHV6, HHV7) AND Viral Monitoring Assay Development (HHV3 (varicella zoster), HHV6 (roseola), HHV7 (cofactor CMV), polyoma JC, WC,KI): PLASMA	5mL PPT Tube OR plasma collected from the CPT tubes for Intracellular Cytokine Staining Viral Phenotyping			X		Х				X		Х				Х	Х

1. If a subject develops anti-donor alloantibodies or de novo anti-HLA (PRA >25%), the test must be repeated on a fresh sample and confirmed within 4 weeks.

2. For Cause Biopsy specimens should be collected at times of graft dysfunction, and prior to initiating therapy.

3. If blood samples are collected for a For-Cause biopsy AND are within 2 weeks of a scheduled visit, then the samples will also be used for the scheduled visit.

4. The first dose of NULOJIX® (belatacept) will be administered approximately 24-48 hours after the last dose of Thymoglobulin® (Anti-Thymocyte Globulin- Rabbit).

5. The results of the non-HLA Ab/Anti-HLA Antibodies/DSA drawn at week 36 will be sent back to the clinical sites in order to make a decision regarding tacrolimus withdrawal at week 40.

6. At week 40, subjects eligible for withdrawal will be weaned over a 4-8 week period based on the protocol.

7. Tacrolimus dosing will be collected following week 44 on subjects who were not eligible for withdrawal or failed withdrawal.

8. During tacrolimus weaning and for 6 weeks post tacrolimus withdrawal, subjects will have weekly labs that include serum creatinine, fasting glucose, amylase and lipase.

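### The only sensitivity analyses certain to be run on week-52 eGFR do not vary the MAR assumption, and the week-36 carry-forward imputes a pre-weaning value for weaned subjects who lack a week-52 result

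*Combined protocol and SAP*

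**What the plan says.** Section 13.2.1 compares the arms on week-52 eGFR in a mixed model in which "repeated measures of eGFR at weeks 4, 12, 28, 36 and 52 will be modeled as a linear function of time". It claims protection against dropout bias on condition that dropout is MAR. It plans to assess MAR before fitting the model; the reference list (reference 28) shows from its title that the method is a local-sensitivity index for nonignorable dropout. If MAR fails, alternatives such as pattern-mixture modelling are to be considered.

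Two sensitivity analyses follow. The first will "replace the missing week-52 values with the corresponding nonmissing week 36 values of each subject", leaving out anyone who has neither value. The second keeps completers only. Both reappear in Table 9. The plan introduces them with the remark that "A number of studies have shown RMANCOVA to be superior to analyses of completers or of data with LOCF imputations".

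On timing, footnote 6 of Appendix 2 states: "At week 40, subjects eligible for withdrawal will be weaned over a 4-8 week period based on the protocol". Section 8 limits weaning to investigational-arm subjects who meet every listed criterion, and Section 4 rules it out in the control arm. The amendment text at the front of the protocol stops further withdrawals.

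**The concern.** A sensitivity analysis for missing data should show how far the conclusion depends on the assumption made about the missing values. Neither named analysis does this. Completers-only drops the subjects in question. Carry-forward replaces MAR with another untested assumption, that nothing changed between week 36 and week 52. If both agree with the mixed model, that agreement is not evidence for MAR.

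The choice of week 36 adds a difficulty specific to this trial. Week 52 is the only modelled visit after weaning begins. A carried week-36 value assumes no change over the interval that contains withdrawal, a step that only one arm undergoes. Any gain from stopping tacrolimus, or any injury after stopping it, is removed for that subject. Such change is plausible on the protocol's own account: Section 2.2.2 reports that in the predecessor study two of four rejection episodes in one group came shortly after tacrolimus was withdrawn.

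**Working it through.** eGFR is in mL/min per 1.73 m², written mL/min here.

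**1. The plan's own figure.** Section 13.3 works "With the sample sizes fixed, a priori, at 30 subjects in each of the two treatment arms" and "with 80% power and Type I error rates of 0.05 and 0.10", for SDs of 16, 20 and 24. By the normal approximation, the detectable difference at SD 20 and two-sided alpha 0.05 is 20 × √(2/30) × (1.960 + 0.842) = 14.47. By noncentral t with 58 df, the results for SD 16 / 20 / 24 are:
- alpha 0.05: 11.77 / 14.71 / 17.65
- alpha 0.10: 10.39 / 12.99 / 15.59

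Rounded up to the next 0.5, these give all six entries of Table 11 (12.0 / 15.0 / 18.0 and 10.5 / 13.0 / 16.0). No stated figure is in error.

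**2. Timing.** Modelled visits are weeks 4, 12, 28, 36 and 52. Weaning starts no earlier than week 40, so week 36 precedes it by at least 4 weeks. Weaning lasts 4–8 weeks and, if on schedule, ends at week 44–48. Week 52 is then 4–8 weeks after its end. A weaned subject who misses week 52 contributes pre-weaning data, or nothing, to the mixed model and to both sensitivity analyses.

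**3. Size of the carry-forward error.** The documents give no dropout rate and no expected change after withdrawal, so both are assumed. With k of 30 missing and a true change D from week 36 to week 52 in those subjects:

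error in the arm mean = −(k/30) × D

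For k = 3:
- D = −10: 3 × 10/30 = 1.0 too high
- D = −20: 3 × 20/30 = 2.0 too high
- D = −30: 3 × 30/30 = 3.0 too high
- D = +10: 1.0 too low

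Six missing doubles these figures and nine triples them.

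**4. Can the two analyses reveal such a fall?** Simulation of 5,000 trials per row, 30 per arm, both arms with mean 60, SD 20 and week-36-to-52 correlation 0.8. Missing values are in the investigational arm only and unrelated to the week-36 value. All of these are assumptions. The MAR column is a regression on week 36, standing in for the mixed model. Entries are mean between-arm differences at week 52.

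| Missing | True fall | Full data | Carry-forward | Completers | MAR regression |
|---|---|---|---|---|---|
| 10% | 10 | −0.87 | 0.14 | 0.13 | 0.13 |
| 10% | 20 | −1.99 | −0.01 | 0.00 | −0.01 |
| 20% | 20 | −3.94 | 0.07 | 0.05 | 0.07 |
| 30% | 20 | −6.04 | −0.05 | −0.04 | −0.05 |

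The three methods agree with one another and all miss the full-data result.

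**5. What a tipping-point analysis would report.** Section 13.2.1 says "All tests of significance will be two-tailed at the 0.05 level". At SD 20 and 30 per arm, the smallest significant difference is 2.002 × 20 × √(2/30) = 10.34. An observed difference of 12 loses significance when the missing investigational values lie below their imputed values by (12 − 10.34)/(k/30):
- k = 3: 16.6
- k = 6: 8.3
- k = 9: 5.5

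An observed difference of 15 needs 46.6 / 23.3 / 15.5. These figures hold the standard error fixed; real multiple imputation adds variance and would tip sooner.

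**The case against.** The strongest reply is that the plan does look at departures from MAR. Section 13.2.1 evaluates the assumption first, by a method aimed at nonignorable dropout, and names pattern-mixture modelling, the family to which a delta adjustment belongs. It does not present the two further analyses as tests of MAR: it ranks them below the primary model and labels them as additional secondary analyses. A reader might infer that departures from MAR go unassessed, and the text does not support that. What remains is that no threshold defines failure, no model or shift range is given, and the alternative is only to be considered.

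The second reply concerns who would be missing. A reader might picture subjects dropping out because of rejection after weaning. Section 8.5 keeps such subjects on the remaining Appendix 2 visits. Section 8.7 follows those who stop therapy to week 52, and Appendix 4 includes serum creatinine then. This stands and lowers the likely count. Under the Study Definitions and Section 9.1, missing values would come mainly from death, loss to follow-up, withdrawn consent or investigator decision. The last can follow an adverse event or abnormal laboratory value, so it may be related to outcome.

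Third, the pre-weaning point does not touch control subjects or investigational subjects never weaned, and the amendment caps the number weaned. This also stands.

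**Conclusion.** The point holds in a limited form. The two analyses certain to be run do not vary MAR, and for weaned subjects without a week-52 value the carried result predates the withdrawal whose consequences week 52 should capture. On the assumed 3 of 30 missing with falls of 10 to 30, the error is 1.0 to 3.0 mL/min. That is modest beside detectable differences of 12 to 18 at alpha 0.05, and it sits in a supplementary analysis, not in the primary estimate. It could matter for a result near the significance boundary.

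Two stronger readings should be resisted. Carry-forward does not systematically favour belatacept: a rise after weaning would make it understate that arm. Nor does it rest on a stronger assumption than MAR; its assumption is a different one. Completers-only is the analysis that asks for more than MAR. The change is worth making because it is cheap, but nothing here shows the primary analysis to be wrong.

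**What to change.** In Section 13.2.1 and Table 9, replace the week-36 carry-forward with a delta-adjusted multiple imputation of missing week-52 eGFR that is always performed, whatever the MAR index shows. Impute by arm, shift the imputed values in pre-stated steps separately for each arm, and report the shift at which the conclusion changes. Where available, let the weekly creatinine that Appendix 2 (footnote 8) schedules during weaning and for 6 weeks afterwards inform the imputation; on schedule this reaches about week 50–54 (44 + 6 to 48 + 6). Confirm that these results enter the database. State how week-52 eGFR is treated after death or graft failure, which Section 13.2.1 leaves open. Keep the completers analysis as descriptive only.

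The cost is SAP wording, modest extra programming and one more set of results to report. No new data collection is needed.

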1.3 Secondary Objective

The secondary objective is to evaluate whether a NULOJIX® (belatacept) based immunosuppression regimen with minimal exposure to CNIs achieves superior renal function, improves cardiovascular and metabolic risk profiles, and preserves protective immunity in recipients of SPK.

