1.5.3 Measures of Cardiovascular and Metabolic Parameters

The following will be measured at baseline, days 28, 84, and weeks 28, 36, and 52, unless otherwise stated below.

- 1. HbA1c.
- 2. Fasting Blood Sugar (FBS).
- 3. Standardized blood pressure measurement and use of anti-hypertensive medications.
- 4. Fasting lipid profile (Total Cholesterol, non-HDL Cholesterol, LDL, HDL, and triglyceride) and the use of lipid lowering medications at baseline, and weeks 28 and 52.

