It is widely recognized that CNIs are major contributors to the principal causes of the poor longterm results that still plague transplantation - death from cardiovascular disease and posttransplant renal failure, be it of the transplant or native kidneys. In the case of renal transplantation, virtually all patients develop lesions of CNI-induced nephrotoxicity and accelerated renal dysfunction 3. The impact of CNI-induced renal dysfunction is underscored by the well-recognized association between preservation of renal function at one year and longterm graft survival⁴,⁵. In addition to their nephrotoxic properties, CNIs are associated with a number of toxicities that increase the risk of death from cardiovascular disease, a factor that accounts for 45.7% of all graft losses following renal transplantation (USRDS Annual Report 1999). Most importantly, CNI are major contributors to the development of new onset diabetes mellitus (DM), the incidence of which approaches 30% following renal and 20% following liver transplantation ⁶,⁷,⁸. These data suggest that CNI would also have a negative impact on beta cell function following pancreas transplantation, although SPK recipients remain largely dependent on these agents to prevent rejection. Strikingly, new onset DM after renal transplantation is associated with more than a 60% increase in risk of graft failure and an almost 90% increase in risk of death⁹. CNI also cause and exacerbate hypertension and dyslipidemia, both of which are known to accelerate cardiovascular disease¹⁰. Together, these toxicities provide a compelling rationale for the identification of immunosuppressive agents that can replace CNI in maintenance immunosuppressive regimens following SPK.

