5.6 Potential Benefits

Potential benefits of a NULOJIX® (belatacept) regimen include avoidance of long term side effects associated with the prolonged use of CNI, such as nephrotoxicity, hypertension, dyslipidemia, and glucose intolerance, and avoidance of sirolimus-related toxicity such as buccal ulcers and dyslipidemia.

Tacrolimus is known to be directly beta-cell toxic in vitro and in vivo, and has been associated with new onset immunosuppression-related diabetes in non-diabetic recipients of solid organ transplants.

Overall, the administration of thymoglobulin to adult renal transplant patients has been safe and effective. Prolonged depletion of T cells has been achieved but has not been accompanied by increased incidence of opportunistic infection or other serious complications. This treatment has generally led to substantial overall reduction in chronic immunosuppression but not tolerance.

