	Biopsy-confirmed Incidence of an increase of ≥ 1 CAN/IFTA grade, relative to baseline, at each follow-up assessment	Dichotomous (Banff score <1 vs. ≥ 1)	Proportion + 95% CI	Log-binomial or Poisson regression
	Prevalence of CAN/IFTA grades I, II, III at week 52	Dichotomous (1 outcome for each grade)	Proportion + 95% CI	Log-binomial or Poisson regression (1 model per grade)
Incidence and Severity of Rejection and Anti-donor reactivity	Incidence of Acute Rejection (AR) of renal or pancreatic transplant within the first 52 weeks	dichotomous	Proportion + 95% CI	Log-binomial or Poisson regression
	Banff score of the 1 st observed of renal or pancreatic AR within 52 weeks post- transplant	Ordered categories (3 levels)	Proportion + 95% CI	Proportional Odds model
	Highest Banff score observed within 52 weeks post-transplant for either renal or pancreatic transplant	Ordered categories (3 levels)	Proportion + 95% CI	Proportional Odds model

Page 85 of 104

Response type	Response	Measurement Scale	Summary Statistics	Models to test for treatment effects
	Steroid vs. nonsteroidal treatment for renal or pancreatic AR	dichotomous	Proportion + 95% CI	Log-binomial or Poisson regression
	Prevalence of anti- donor HLA antibodies at week 52 for renal or pancreatic transplant subjects	dichotomous	Proportion + 95% CI	Log-binomial or Poisson regression
Cardiovascular + Metabolic	Fasting blood sugar	continuous	Mean and/or geometric mean + 95% CI	Separate ANOVA or ANCOVA at weeks 28 and 52
	HbA1c (baseline through week 52)	continuous	Mean and/or geometric mean + 95% CI	Mixed effects Repeated Measures ANCOVA
	Blood pressure at weeks 28 and 52	Continuous	Mean and/or geometric mean + 95% CI at weeks 28 and 52	ANCOVA at weeks 28 and 52, with use of blood-pressure drugs as a covariate
	Use of BP medications	dichotomous	Proportion + 95% CI	Log-binomial or Poisson regression
	Fasting lipid profiles at weeks 28 and 52	Continuous	Mean and/or geometric mean + 95% CI	Separate ANOVA or ANCOVA at weeks 28 and 52
	Total daily pill count	continuous	Mean + 95% CI tabulated and plotted over time, by trt. group	Separate ANOVA or ANCOVA at day 85 and weeks 28 and 52 (or Poisson Reg)
Safety (for both renal and pancreatic transplant subjects)	Incidence of death or graft loss or undetectable C-peptide separately and as a composite	dichotomous	Proportion + 95% CI	Log-binomial or Poisson regression
	Incidence of any AE	dichotomous	Proportion + 95% CI	Log-binomial or Poisson regression

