Appendix 1: Schedule of Events – Pre-Transplant to Day 4 Post-Transplant (Visit 1)

Screening Assessments	Window
 Blood Type (A, B, O), Rh Factor HLA Typing (Class I: A, B, C, Class II: DR, DP, DQ) Peak PRA, Current PRA or cPRA (within 12 months prior to transplant), Crossmatch Hepatitis B, Hepatitis C, and HIV test results Last reported CMV (IgG, IgM and/or total CMV Ab) and EBV testing (IgG, IgM) Tuberculosis testing (within 12 months prior to transplant). If documentation is not present at the time of transplant, and the subject does not have any risk factors for TB, a TB-specific interferon gamma release assay (IGRA) may be performed. 	Retrospective data collection, no time limits unless specified. Repeat only if not available.
 Informed Consent and Assessment of Eligibility Demographics Medical History, Physical exam (BP, Pulse, Temperature, Respiration, Weight) Concomitant Medications Local Labs: Serum Pregnancy Test, Hematology Panel (CBC, differential, platelets), Chemistry 12-Panel / CKD-EPI equation, MDRD 4 variable, Serum Amylase, Serum Lipase, Fasting Lipid Panel (Total, HDL, LDL, Triglycerides), Hemoglobin A1c, Urinalysis 	Within 30 days prior to transplant, until time of transplant.
 Flow Cytometry (20mL blood in Cyto-Chex Tube) Intracellular Cytokine Staining – Viral Phenotyping (32mL blood in CPT Tube) Markers of Autoimmunity – PBMC (30mL blood in Green-top Tube) Markers of Autoimmunity – serum (5mL blood in Red-top Vacutainer) Gene Expression, mRNA profiling in blood (2.5 mL blood in PAXgene RNA tube) Cytokines and Growth Factors- serum (7mL blood in Red-Top Vacutainer) Serum Proteins – CTGF, TGFbeta (4.5mL blood in CTAD) Urine Proteins – CTGF, TGFbeta (supernatant) Gene Expression, mRNA profiling in urine (urine pellet) Non-HLA Ab, Anti-HLA Ab, DSA (5mL blood in Red-top Vacutainer) Genomics- gene polymorphisms (4mL in Lavender-top EDTA Vacutainer) Viral Monitoring by PCR (CMV, BKV, JCV, HHV6, HHV7) and Viral Assay Development (HHV3- varicella zoster, HHV6- roseola, HHV7- cofactor CMV, polyoma JC, WC, KI).(plasma from ICS sample) 	Within 48 hours prior to transplant
 Randomization (RhoRand System) Assessment of Events: AE/SAE Solumedrol®(Methylprednisone) : 500mg – Intraoperatively Thymoglobulin® (Anti-thymocyte Globulin – Rabbit) Prograf® (tacrolimus) CellCept® (mycophenolate mofetil) 	Day of Transplant
 Methylprednisolone 250 mg Thymoglobulin® (Anti-thymocyte Globulin – Rabbit) 	Day 1 Post-Transplant

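### Table 9's only blood-pressure test adjusts for BP-drug use without saying when it is measured; if on-study use is meant, it does not estimate the regimen's total effect

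*Combined protocol and SAP*

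**What the plan says.** Table 9 (section 13.2.2, Cardiovascular + Metabolic block) has one row for blood pressure as an outcome. Its listed test is "ANCOVA at weeks 28 and 52, with use of blood-pressure drugs as a covariate". The summary column gives arm means with 95% confidence intervals, but no test without the drug covariate is listed.

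The following row, "Use of BP medications", treats drug use as a dichotomous outcome compared between arms by log-binomial or Poisson regression. No timing is given there either.

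Section 1.5.3 lists "Standardized blood pressure measurement and use of anti-hypertensive medications" as a single item, measured at baseline, days 28 and 84, and weeks 28, 36 and 52. Appendix 2 records antihypertensive drugs at every year 1 visit. Appendix 1 collects concomitant medications and "Medical History, Physical exam (BP, Pulse, Temperature, Respiration, Weight") before transplant. Both pre-transplant and on-study drug use are therefore available as the covariate.

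The objective served is section 1.3, which asks whether the belatacept regimen "improves cardiovascular and metabolic risk profiles".

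**The concern.** The plan's own premises make on-study antihypertensive use a variable that treatment can affect. Section 2.1 states "CNI also cause and exacerbate hypertension and dyslipidemia". Section 5.4.2 lists hypertension among tacrolimus side effects. Section 5.6 names as a potential benefit of belatacept the "avoidance of long term side effects associated with the prolonged use of CNI, such as nephrotoxicity, hypertension, dyslipidemia". Section 8 sets different tacrolimus trough targets by arm. The trial is also open label (section 10.4.1), so prescribing could differ by arm for reasons other than measured BP.

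Holding such a variable fixed changes the question. The objective concerns what happens to BP when a patient is assigned one regimen rather than the other, including any change in the antihypertensives then needed. The adjusted model instead compares patients with the same drug status at the visit, and those groups are no longer formed by randomisation alone.

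While the timing stays open, it can also be settled after the data are seen.

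**Working it through.** **No plan figure to reproduce.** The documents give no BP standard deviation, effect, drug-use rate or power. The sample size (30 per arm, section 13.3) and the 0.05 level (section 13.2.2) come from the plan. All other inputs below are assumptions.

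**Why the two effects differ.** Fit BP on arm and drug use by least squares. With b_arm the adjusted effect, b_drug the drug coefficient, and p1 and p0 the proportions on drugs in the belatacept and control arms:

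unadjusted effect = b_arm + b_drug × (p1 − p0)

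The effects agree if p1 = p0 or b_drug = 0. Randomisation makes p1 = p0 on average for pre-transplant use, but not for on-study use.

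**First illustration: prescribing shifts directly with arm and does not depend on BP.** Assume a true effect on untreated systolic BP of −8 mmHg, a drug effect of 10 mmHg and 50% of controls treated.
- 30% of the belatacept arm treated: unadjusted = −8.0 + (−10) × (0.30 − 0.50) = −6.0 (power 30%); adjusted −8.0 (51%).
- 70% treated: unadjusted = −8.0 + (−10) × (0.70 − 0.50) = −10.0 (68%); adjusted −8.0 (50%).

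The direction of the shift is therefore not fixed.

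**Second illustration: prescribing depends on BP.** Assume an untreated SD of 15 mmHg, a true effect of −4 or −8, a drug effect of 5, 10 or 15, half of controls treated, and a logistic probability of treatment with slope per SD of untreated BP (simulation, 2,000,000 subjects per setting).

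| Logit slope per SD | Adjusted ÷ unadjusted effect |
|---|---|
| 0.3 | 1.00 to 1.06 |
| 1 | 0.89 to 1.04 |
| 2 | 0.71 to 0.91 |
| 4 | 0.54 to 0.74 |

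For a true effect of −8 and a drug effect of 10, with 30 per arm and each model using its own standard error:

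| Slope | Unadjusted (power) | Drug-adjusted (power) |
|---|---|---|
| 1 | −6.9 (48%) | −6.7 (45%) |
| 2 | −6.4 (49%) | −5.1 (35%) |
| 4 | −6.1 (49%) | −3.8 (27%) |

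Over all settings, the power change (adjusted minus unadjusted) is −6 to +9 points at slopes 0.3 to 1 and −24 to −2 points at slopes 2 to 4. The largest loss (true −8, drug effect 5, slope 4) is −7.1 (52%) against −3.9 (27%). At a true effect of −4 with drug effect 10, power is 16% against 15% at slope 1 and 16% against 10% at slope 4.

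**Separate check of the principle.** A second simulation used another prescribing model (1,000,000 subjects per setting; regimen effect 0, −5 or −10; drug effect 0 to 15; slope 0.05 or 0.15 per mmHg). Its slopes should not be equated with those above.
- Covariate fixed before randomisation: ratio 1.00 in every setting with a treatment effect.
- On-study covariate: ratio 0.71 to 1.15. For example, adjusted −3.57 with b_drug 11.45 and use 0.37 against 0.50 gives −3.57 + 11.45 × (−0.13) = −5.06, against −5.02 computed directly (the use rates are rounded). At the other end, −3.55 + (−3.56) × (−0.13) = −3.09, against −3.10 directly.

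**Null case.** If treatment affects neither BP nor drug use, both tests reject in 5.0 to 5.2% of trials.

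**Proposed replacement.** Adjusting for pre-transplant BP keeps the unadjusted effect (−6.9 at slope 1, −6.1 at slope 4). Its power is 51–52%, 58–59% and 72–74% for an assumed baseline correlation of 0.3, 0.5 and 0.7.

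**The case against.** **Pre-transplant use may be meant.** It is collected, so the established fault is an undefined covariate. This stands, and in that case the remedy is one clause. The word baseline alone would not settle it, because section 13.1 can be read as attaching that label to day 28, which is after randomisation.

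**The material effect needs strong assumptions.** At slopes of 1 or less the difference is small, and at a true effect of −4 power is low with either model. This stands as a limit on size. It does not change which quantity is estimated.

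**The treatment contrast is narrower than the background suggests.** Both arms take tacrolimus at week 28. Withdrawal was planned only from week 40 in eligible subjects, and the amendment at the front of the document halts it and moves the experimental arm to physician-directed therapy. This makes a large effect on prescribing less certain but does not rule one out: section 8 still sets trough targets of 5–8 against 3–5 ng/ml after week 24.

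**Adjustment removes the masking effect of drugs.** A yes/no covariate does not do so reliably. With a true untreated effect of −8 and slope 4, the adjusted estimate of −3.8 is further from −8 than the unadjusted −6.1.

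**Readers still see arm means and drug use by arm.** True, and this limits the harm. But section 13.2.2 makes the listed model the test of treatment difference.

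**Conclusion.** The concern holds as a conditional one. The timing of the covariate is not stated. If on-study use is meant, the only listed BP test does not estimate the total effect of the assigned regimen. Under the assumed inputs the practical difference is small when prescribing follows BP weakly or moderately, and material when prescribing is close to a threshold rule. Its direction cannot be known in advance.

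The reach is one of 28 secondary endpoints, through one model run at two time points. The change should be made, but it does not threaten the trial's main conclusion. Confidence is medium, because the intended timing is unknown and every BP input is assumed.

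As a side note, section 1.5.3 pairs lipids with lipid-lowering drug use in the same way, yet the row "Fasting lipid profiles at weeks 28 and 52" names no drug covariate. The two parallel items are handled differently without explanation.

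**What to change.** 1. State in Table 9 when BP-drug use is measured, naming Visit 1 (pre-transplant) or the specific study visit.
2. Make the main BP comparison at weeks 28 and 52 an ANCOVA without on-study drug use, adjusted for Visit 1 BP and, if wanted, pre-transplant BP-drug use.
3. Keep on-study BP-drug use as its own endpoint and report it beside the BP result.
4. Label any model adjusted for on-study drug use as supportive, with its timing stated.
5. As a clarification only, reconcile Appendix 4, whose medication row covers only immunosuppressive drugs, with section 8.3, which has centres record non-immunosuppressive therapy too. It should be clear whether antihypertensive use is recorded for subjects on reduced follow-up.

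Items 1 to 4 cost Table 9 and SAP wording only, because Visit 1 BP and medications are already collected. They should be written in before database lock: section 13.7 has the final analysis report the original SAP and label additions ad hoc. If subjects on reduced follow-up turn out to lack antihypertensive data, past visits would need retrieval from records, since the version 7.0 footer is dated June 28, 2016 and study completion is August 31, 2016.
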